Endpoint	The primary outcome will be the percentage of swallows with aspiration and/or penetration for cold milk compared with room temp milk (a total of 15 swallows will be assessed by VFSS and FEES). Based on our preliminary results, we expect to find a significant decrease in penetration and aspiration during the initial cold swallows (5 swallows). We expect this improvement to be sustained on the subsequent cold swallows (10 swallows) following the 15-minute cold liquid feeding. A decrease of 30% in penetration and/or aspiration with cold milk will be considered significant. Similarly, a 30% improvement of feeding coordination as assessed by nFant device will be considered significant.
	2. Evaluate the safety of feeding cold milk in preterm infants. We will evaluate whether cold milk will cause hypothermia (assessed by measuring Axillary temperatures), change in vital signs (respiratory rate, heart rate, and oxygen saturation) as well as change in mesenteric blood flow indices (assessed by abdominal ultrasound) These changes with cold milk feeding will be expressed as % change compared to base line (room temp milk).
Study Duration	2 years
Participant Duration	The subjects will participate in the study for approximately 48 hours during their NICU hospital stay
Population	Preterm Infants less than 34 weeks gestation admitted to NYU- Langone Long Island Hospital NICU. (n=42)
Study Sites	NYU- Langone Long Island Hospital
Number of participants	42

1. Introduction, Background Information and Scientific Rationale

Approximately half a million preterm infants are born every year in the USA.^{1,2} It is estimated that 30-70% of very low birth weight (VLBW) preterm infants will be diagnosed with swallowing dysfunction (dysphagia), with an inverse relationship between the severity of dysphagia and gestational age (GA).³⁻⁶ Although the pathophysiology of dysphagia is multifactorial,^{4,7-9} the discoordination between swallowing and breathing is the most prevalent cause of dysphagia in preterm infants,¹⁰ which often leads to airway compromise in the form of laryngeal penetration and/or tracheal aspiration into the lungs.^{7,11} Chronic airway compromise results in a persistent inflammatory state, with disease progression to chronic lung injury and *bronchopulmonary dysplasia (BPD)* that can be devastating for already fragile and developmentally immature lungs in preterm infants.^{4,7}

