Radiation Exposure - For this study, we aim to visualize 15 swallows, which will take approximately 18 seconds. Compared to the typical range of radiation time of 90-180 seconds in routine VFSS. The radiation exposure related to this research equals 10-20% of what an infant would be exposed to during a typical routine VFSS.

Radiation Exposure Prevention – Our study design will include various radiation sparing techniques: 1) Commination, which restricts the x-rays to a smaller area on the subject; 2) Pulsed fluoroscopy, which takes 30 frames/second, instead of the continuous fluoroscopy of 60 frames/second; 3) The radiologist will utilize intermittent fluoroscopy to turn the radiation on only at the time of swallowing; 4) A lead shield will be placed on the subjects' lap to protect reproductive organs from radiation scatter.

Known Potential Benefits

The subjects may or may not personally benefit from being in this study. The results of this research (the safety and effectiveness of cold milk for each subject) will be disclosed to the medical team for further consideration. If the

results confirm safety and efficacy for that infant, the medical team can consider using cold milk to treat the infant's dysphagia which can be a significant benefit to the subject.

3. Objectives

The first objective is to identify preliminary evidence for the efficacy of feeding full oral cold milk for dysphagia management in preterm infants. We hypothesize that oral feeding of cold milk in preterm infants with dysphagia will improve suck/swallow/breathe coordination and decrease penetration/aspiration to the airway. Our second objective is to confirm the safety of this practice. We hypothesize that cold milk intervention will have no adverse effects on intestinal blood flow as assessed by Doppler Ultrasound. These objectives are significant because there is a critical need to identify effective and safe evidence-based treatment options for dysphagia management in preterm infants.

4. Study Design

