This will be a prospective study, with each infant serving as their own control. All study subjects will meet the inclusion/exclusion criteria listed in Section 5 of this proposal and informed consent will be obtained. The subject will be considered for the study if the medical team diagnosed the infant with clinical dysphagia and decided to obtain Video Fluoroscopic Swallow Study (VFSS), or Fiberoptic Endoscopic Evaluation of Swallowing [FEES) or both to help manage the dysphagia (such as delay oral feeding till the child is more mature or use feeds thickeners). The VFSS and FEES are not a requirement for step 1 however abnormal VFSS and FEES are requirement for step 2.

The following study procedures will be done before the routine VFSS/FEES testing ordered by the medical team:

Study Protocol Timeline

• Step 1 (bedside procedures):

- We will evaluate the infant's sucking, swallowing, and breathing patterns using a non-invasive FDA approved equipment (nFant® Feeding Solution). This device is in clinical use for several years and routinely used in several NICUs. The nFant has a wireless sensor within the nipple to assess sucking and swallowing coordination during feeding. This machine is not routinely used in NYU- Langone Long Island Hospital NICU because of costs but will be available only for infants enrolled in this research study. The nfant assessments will be performed by the research team under two separate feeding conditions, standard room temperature (RTS) and cold temperature (CS, at 4-9°C) of milk/formula for an entire feeding (15-20 minutes). The two feedings will be done on the same day but may not necessarily be two consecutive feedings (depending on the baby's eagerness to feed orally). The order of each condition will be randomized to control for fatigue. Inter- and intra-rater reliability measures will be calculated. The nfant assessments will include the following measurements:
 - peak amplitude the displacement of the nipple during compression phase normalized from a calibrated 0% to 100%;
 - duration how long or drawn out sucking events are from onset to end in seconds;

- frequency the rate at which consecutive suck events are occurring in Hertz;
- > suck bursts number of sucks per burst, duration and number of bursts, and active time spent sucking;
- > suck smoothness the number of velocity changes in a nipple amplitude trace during a suck.

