 - If the dysphagia didn't improve, the study would end, and the child will no longer be eligible for participation further in this research study.
 - If the dysphagia improves with cold liquid, VFSS will then be turned off and the infants will then be fed their regular feeds (formula or expressed breast milk as indicated by the medical team) chilled to an approximate temperature of 4-9°C for a total of 15 minutes, or until the infant shows signs of feeding completion. The cold feeding will be replaced every 5 minutes to make sure that the temperature is maintained at 4-9°C to minimize habituation effect.³⁰
 - After the 15 minute period, the infant will be re-assessed by VFSS-FEES using cold barium from the same bottle (10 swallows, labeled "Cold Swallows-2" [CS2]). This design evaluates whether a full feeding of cold liquid will result in decreased penetration or aspiration compared to RTS condition. These 10 swallows assessment are done for the research purpose only).
 - The axillary temperature will be monitored every 10 minutes. Infants' vital signs (blood pressure, respiratory rate, heart rate, and oxygen saturation), as well as evidence of any respiratory compromise, will be recorded. A neonatologist will be next to the baby at all times. The baby will return to the NICU after the study accompanied by the NICU team, including the neonatologist.

Study #: i20-00876

Version Date: 6/13/2022

Depending on the scheduling of the VFSS/FEES testing by the infant's medical team, the research team might need to do Step 2 before Step 1, as described above. There will be at least 24 hours period between the two steps.

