The results of the testing with cold milk will be disclosed to the medical team. The research team is ethically obliged to disclose the results of efficacy and safety of cold milk use in each child to their treating team. The medical team can decide if that will be an option for dysphagia treatment. The research team will not interfere with that decision. Of note, the results of this research requires enrollment of 42 infants to test the hypothesis that cold milk is effective and safe for dysphagia in preterm infants. If efficacy and safety are demonstrated, clinicians can use cold milk without the need to do all the safety and efficacy measures detailed in this study for each child in the future. However, for the participants in this study, if efficacy and safety is demonstrated for that particular child, it will be safe to use cold milk for that specific child if the medical team desires. However again, the medical team will decide to use this information or not to treat dysphagia. We also changed the protocol so the results of this research can be disclosed to the family by the clinical team only.

Data collection sheets will be immediately labeled with a unique identifier with no identifying or protected information. Consent forms and data collection sheets will be kept in a secure location for up to six years in accordance with institutional policies. Digital images obtained from VFSS and FEES procedures will be saved onto a writable DVD and immediately labeled with a unique identifier with no link to identifying or protected information. In order to minimize loss of patient confidentiality, all participant data forms will be coded with a subject ID number and will not contain the name, medical record number, date of birth, or other identifiable information. A master spreadsheet that links the study number to the medical record number will reside on REDCap.

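### The conclusion that cold milk is safe for an individual child, and usable in future children without the study's measures, goes beyond what one or two observed cold feeds can support

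*Combined protocol and SAP*

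**What the plan says.** Three statements set out what the trial is meant to conclude.

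- Section 4, paragraph on disclosing cold-milk results to the medical team: "if efficacy and safety is demonstrated for that particular child, it will be safe to use cold milk for that specific child", should that team wish to.
- Same paragraph, on a positive result in the 42 infants: "clinicians can use cold milk without the need to do all the safety and efficacy measures detailed in this study for each child" in future.
- Section 3 (Objectives): "Our second objective is to confirm the safety of this practice". The Brief Summary in the synopsis instead describes the evidence sought, on efficacy and safety alike, as preliminary.

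Section 2 (Known Potential Benefits) and Section 5 (Vulnerable Subjects) tie the possible benefit to the child to results that confirm safety and efficacy for that infant.

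The exposure behind these statements is short. The synopsis says "The subjects will participate in the study for approximately 48 hours during their NICU hospital stay". Step 1 has one room-temperature and one cold bedside feed of 15 to 20 minutes. Step 2 has a second cold feed, "chilled to an approximate temperature of 4-9°C for a total of 15 minutes, or until the infant shows signs of feeding completion", but only after a positive VFSS/FEES and improvement on the first five cold swallows (CS1). Otherwise, "If the dysphagia didn't improve, the study would end" for that child. The safety analysis is a two one-sided test (TOST) on the 90% confidence interval of the pre-post change.

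**The concern.** The use under discussion is treatment of dysphagia, which a treating team would ordinarily read as feeding cold milk more than once or twice. The trial observes one or two cold feeds with short follow-up, and its safety test speaks to an average over infants. Neither supports a statement that the practice is safe for a named child, and neither supports dispensing with monitoring in later children.

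This matters during the trial as well as at its end. Each child's results go to the treating team, which may act on them. Section 5 also uses the expected child-level result to support possible direct benefit in a study that it says may exceed minimal risk. If the condition for that result is undefined, that part of the justification rests on a conclusion the data cannot deliver.

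**Working it through.** **1. Exposure and follow-up (Section 4, Steps 1 and 2; Safety Monitoring Plan).** In the listed order of steps:

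- Cold feeds per infant: one at the bedside, plus one more if VFSS/FEES is positive and CS1 improves, so one or two.
- Doppler: one hour before, and 30 and 60 minutes after, each bedside feed. One cold feed is covered; the Step 2 cold feed is not.
- Axillary temperature: Step 1, before and after each feed, then 10 and 30 minutes after the cold feed. Step 2, every 10 minutes, with no stated end.
- Adverse vital-sign data: recorded continuously during the cold feed, about 15 minutes.

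**2. The plan's own safety figure.** Power above 80% is stated for TOST with N = 42, margin ±0.5°C and true difference 0. No standard deviation (SD) is given, so the figure cannot be reproduced. By simulation (20,000 runs), power is about 98% at an SD of change of 0.8°C, 81% at 1.08°C and 69% at 1.2°C. The point here does not depend on this, because even a successful test is a statement about the mean.

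**3. Group mean against one child.** Assume normal changes with true mean 0. The share of infants whose change exceeds ±0.5°C is 2 × [1 − Φ(0.5/SD)]:

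- SD 0.3°C (assumed): about 10%.
- SD 0.5°C (assumed): 2 × [1 − Φ(1)], about 32%.

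At SD 0.5°C the simulated power with 42 infants is about 100%. Equivalence would almost surely be declared while about a third of infants had individual changes outside the margin. Some of that spread would be measurement noise, and such a change is not in itself harm. The calculation shows only that group equivalence does not establish equivalence for a given child.

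**4. Best case for the group: no events.** The one-sided 95% upper limit for 0 events in n is 1 − 0.05^(1/n):

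- n = 42 (planned enrolment, all having the bedside cold feed): 1 − 0.05^(1/42) = 6.9%.
- n = 30 (the plan's stated number with a positive test): 9.5%.
- n = 25 (the N in the power calculation; also 42 × 0.60 = 25.2): 1 − 0.05^(1/25) = 11.3%.

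Put another way, a true per-infant risk of 2% would produce no event in 42 infants with probability 0.98^42 = 43%, and a risk of 5% with probability 0.95^42 = 12%.

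**5. Best case for one child.** Two event-free feeds leave an upper limit on per-feed risk of 1 − 0.05^(1/2) = 77.6%; one feed leaves 95%. Taking feeds as independent, a child with a true per-feed risk of 20% would pass both with probability 0.8² = 64%. For swallowing, 0 events in 15 cold swallows leaves 1 − 0.05^(1/15) = 18.1%. That treats swallows as independent at a constant rate and ignores that only infants who improved at CS1 reach the last ten, so it is favourable.

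None of these limits says anything about repeated cold feeding.

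**The case against.** Several parts of the defence stand.

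- **The statements are conditional.** A reader might infer that the protocol promises cold milk will prove safe. It does not: both sentences begin with an if, and the treating team decides. The difficulty is that the condition has no definition at the level of one child.
- **The sentence on dispensing with measures concerns future children** and rests on the 42-infant result, not on one child's feeds. That result still covers acute exposure only.
- **Per-infant thresholds exist.** A reader might infer that the plan has no individual criterion at all. The Safety Monitoring Plan lists six events during cold feeding that end participation for that baby. They are stopping rules during a feed, do not cover blood flow, and do not define demonstrated safety.
- **The conflict over preliminary evidence is narrower than it looks.** In Section 3 the word belongs to efficacy: "The first objective is to identify preliminary evidence for the efficacy of feeding full oral cold milk for dysphagia management". Only the Brief Summary applies it to safety, so the conflict lies between that summary and Sections 3 and 4.
- **What families are told is not documented.** A reader might infer that parents receive the overstated conclusion. The consent pages are not available, disclosure to families is left to the clinical team, and Section 2 says that a subject may or may not benefit.
- **The Introduction frames the gap as a full-duration feed**, after earlier work on five swallows. Testing one full feed is a legitimate aim. It supports a claim about a full feed, not about continuing treatment.

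**Conclusion.** The point holds as a mismatch between stated conclusions and design. The design can show acute tolerance and a short-term swallowing effect over one or two cold feeds. It cannot show that cold milk is safe for a particular child, confirm the safety of the practice, or by itself justify omitting the measures in later children. With no events, per-infant risks up to 6.9% (42 infants) or 11.3% (25 infants) remain compatible with the data for this acute exposure, and repeated feeding is unobserved.

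The limits assume independent infants and that every infant counted had a cold feed. Section 4 allows Step 2 before Step 1, and an infant stopped at Step 2 might then miss the bedside feed, so 42 is the favourable case. The figures in item 3 rest on assumed SDs; the conclusion does not. The documents do not show that cold feeding is unsafe or that the trial should not run. No endpoint, analysis or sample size needs to change on this account.

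**What to change.** Reconcile Sections 2, 3, 4 and 5 with the Brief Summary:

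- In Section 3, and in the benefit statements of Sections 2 and 5, limit the conclusion to preliminary evidence of acute tolerance and short-term swallowing effect over one or two cold feeds.
- In the Section 4 disclosure paragraph, say that the treating team receives that child's observations with their limits: events out of swallows from Step 2, Doppler from Step 1, and temperatures and vital signs from each step. State that this is not a conclusion that cold milk is safe for that child. Whether to use it stays with the treating team.
- Qualify the sentence on future use by saying that repeated cold feeding was not studied.

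Follow-up of diagnoses such as necrotising enterocolitis through chart review is not part of this change. The plan has no item recording later cold-milk use and no follow-up window, so it would be a new component.

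The cost is a wording amendment and a narrower claim.

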- The axillary temperature will be measured immediately prior to and after each feeding condition. It will also be measured at 10, and 30 minutes after the CS feed, at the same time the gastric content temperatures are taken. Infants' vital signs will be recorded (blood pressure, respiratory rate, heart rate, and oxygen saturation), as well as evidence of bronchospasm, lethargy, respiratory distress, apnea, tachypnea, cyanosis, bradycardia, or tachycardia.
- Doppler ultrasound (Sonosite Edge Ultrasound system, Sonosite, Inc, WA) will be used to measure
 intestinal blood flow indices including the superior mesenteric artery flow (SMA), peak systolic velocity,
 SMA mean velocity, SMA end-diastolic velocity, resistive index, pulsatility index, portal vein volumetric
 blood flow, as well as heart rate and mean arterial blood pressure. Intestinal blood flow monitoring via
 Doppler ultrasound will be performed 6 times for each participant, performed one hour before and at 30 and
 60 minutes after both bedside feeding conditions (RTS and CS). Measurements will be taken at the bedside
 in the supine position.
- Step 2 (done 24-48 hours after step 1):
 - Infants will be transported to the radiology suite and undergo VFSS and or FEES, as ordered by the treating
 medical team (Figure1: the blue boxes indicate procedures done for research purpose only. None of the
 research procedures are experimental and are approved tests for neonates including VFSS, FEES, nfant
 test and abdominal ultrasound).
 - Routine procedure for VFSS or FEES will be followed as ordered by the medical team. This procedure is part of the routine clinical care and not considered part of the research study.
 - If no dysfunction is noted, the procedure will end, and the child will no longer be eligible for further participation in this research study. If dysfunction (penetration/aspiration) either on the VFSS or FEES study is noted, the child will be eligible to participate in the next phase of the study.
 - Immediately following the initial VFSS-FEES assessment, the infants will remain in the same seated position with the FEES scope in place. While keeping all variables from the standard VFSS-FEES the same, the infant will be fed cold barium (4-9°C) using the same nipple. A total of 5 swallows will be visualized using VFSS and FEES, labeled "Cold Swallows-1 (CS1)." These 5 swallows assessment are done for the research purpose only.

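### The primary outcome is a visual judgement on swallow images, and the plan does not say who scores it, when, or under what masking

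*Combined protocol and SAP*

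**What the plan says.** - **Outcome.** Synopsis, Endpoint: "The primary outcome will be the percentage of swallows with aspiration and/or penetration for cold milk compared with room temp milk", with the note that "a total of 15 swallows will be assessed by VFSS and FEES". The same row says that the team expects a significant fall on the first cold swallows, and that a 30% decrease will count as significant.
- **Order of conditions.** Section 4, Step 2: the routine study comes first. Then: "Immediately following the initial VFSS-FEES assessment, the infants will remain in the same seated position with the FEES scope in place". Cold barium follows: "A total of 5 swallows will be visualized using VFSS and FEES". These swallows are labelled CS1. If dysphagia has improved, a 15-minute cold feed is given and 10 more swallows are filmed and labelled CS2. If it has not improved, the infant leaves the study.
- **Storage.** Section 4, after the timeline: "Digital images obtained from VFSS and FEES procedures will be saved onto a writable DVD and immediately labeled with a unique identifier". The rest of that sentence and the one after it concern identifying information and confidentiality.
- **Rater quality.** Section 4, Step 1: "Inter- and intra-rater reliability measures will be calculated". This stands in the bullet on the nFant bedside assessment. The only randomisation of order, that of the two bedside feeds, is in the same bullet.
- **Analysis.** Statistical Considerations: a two-sided Wilcoxon signed-rank test compares RTS (room temperature) with CS (cold).

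The text supplied mentions no blinding, masking, independent reader or shuffled review of the swallow images. It gives no scoring rule for penetration or aspiration.

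**The concern.** Whether a borderline swallow counts as a penetration is a matter of judgement. A reader who knows that the swallow is cold, and expects cold to help, may read it more leniently. Such leniency goes straight into the cold-minus-room-temperature contrast that the primary test uses. Using each infant as their own control removes differences between infants, but not a reader's tendency to favour one condition. Rater reliability would not remove it either, since two unmasked readers can agree and share the same bias.

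With few swallows per infant, small changes in reading count for a lot. At stake are the error rate of the primary test and the size of the reported effect.

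**Working it through.** **1. Is the condition known at scoring?** The documents do not say so in words. Four features taken together imply it:

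- the Step 2 order is fixed (routine, CS1, CS2);
- the cold swallows carry condition labels;
- someone must judge on the spot whether cold helped;
- no step hides the condition afterwards.

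The identifier on the DVD is there for privacy, and nothing says that it separates or conceals RTS, CS1 and CS2.

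**2. Reproducing the plan's own figure.** Inputs from Statistical Considerations and Section 6: mean change 30, common SD 25, correlation 0.20, N=25, two-sided alpha 0.05.

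- SD of the difference = 25 × √(2 × (1 − 0.20)) = 31.6.
- Standard error of the mean difference = 31.6 / √25 = 6.32.
- Power by simulation of the Wilcoxon test (10,000 samples): 99.2%. By normal approximation: 99.7%.

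Both agree with the stated figure of more than 95%.

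**3. Weight of one swallow.** One swallow read differently moves an infant's percentage by 100/5 = 20 points, 100/10 = 10 points or 100/15 = 6.7 points, depending on how many swallows form the denominator.

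**4. Effect on the p-value.** The reading shift is an assumption; the documents give none. It is a net average over all infants, always towards cold. With no true effect, N=25 and SD of the difference 31.6:

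| Assumed net shift (points) | Trials with Wilcoxon p<0.05 |
|---|---|
| 0 | about 5% |
| 5 | about 11% |
| 6.7 | about 17% |
| 10 | about 31% |
| 15 | about 60% |

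**5. Adding the synopsis threshold.** The plan does not say whether the 30% decrease is a formal rule, or whether it is absolute or relative. Suppose it must be met as well as p<0.05, again with no true effect. The probabilities below are normal approximations for the observed mean fall; simulations that also required p<0.05 agree closely.

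- *Read as 30 percentage points.* Shift 10: (30 − 10)/6.32 = 3.16, so about 0.08%. Shift 5: (30 − 5)/6.32 = 3.95, so below 0.01%.
- *Read as a relative 30% fall from a 71% baseline.* The baseline is an assumption, taken from the dysphagia occurrence that the Introduction reports for the team's earlier study. The required fall is 0.30 × 71 = 21.3 points. Shift 10: (21.3 − 10)/6.32 = 1.79, so about 4%. Shift 5: (21.3 − 5)/6.32 = 2.58, so about 0.5 to 0.6%.

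**6. If cold truly works as planned.** Power is already about 99%, so a reading shift hardly changes the test. It adds directly to the estimate: a 5-point shift turns a true 30 into 35.

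**The case against.** The strongest reply is that the plan is silent rather than wrong. It does not name who scores the images for research, or whether scoring is live or off-line. The live judgement after CS1 is a go/no-go step and is not stated to be the primary score. Planned intra-rater reliability normally implies repeat reading. This stands to the extent that a reader might infer that the protocol prescribes unmasked scoring, and the documents do not support that. They leave scoring unspecified under conditions that make knowledge of temperature likely. The reliability sentence belongs to the nFant assessment and does not amount to masking.

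A reader might also infer that the images are already coded for masked reading and need only be used. They are not: the code is for privacy, and clip-level codes would be a new step.

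Nor should 11% and 31% be read as the trial's false-positive rate. They rest on assumed shifts, assume no true effect and describe the p-value alone. The synopsis threshold, if binding, cuts them sharply.

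Finally, this is a small own-control study seeking preliminary evidence. That limits how serious the point is, but a remedy this cheap is still worth adopting.

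**Conclusion.** The point holds as a gap in the plan with an inexpensive remedy. A subjective primary outcome has no stated reader, timing or masking, and the Step 2 procedure implies that the condition is known at scoring. Any resulting bias would most likely favour cold.

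Its size cannot be derived from the documents. Under assumed net shifts of 5 to 10 points and no true effect, the Wilcoxon test alone would be significant in about 11% to 31% of trials. With the 30% decrease also required, the range is under 0.1% (as 30 points) or about 0.5% to 4% (as a relative fall from an assumed 71%). In that case the main consequence is an inflated estimate rather than a false positive.

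The conclusion rests on the text supplied. Figure 1 and one removed passage could not be checked. If masked reading is already intended, one sentence naming the reader and the procedure settles the matter.

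**What to change.** State in Section 4 and in Statistical Considerations that the primary score comes from an off-line re-read of the saved recordings by the existing raters. Specify that:

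- RTS, CS1 and CS2 recordings are cut into clips of equal length and the same modality, so that neither the number of swallows nor VFSS versus FEES reveals the condition;
- each clip has its own code without a condition label, and clips are shuffled across infants;
- the live reading still serves clinical care, Step 2 entry and the decision after CS1;
- no infant is removed because the masked score differs from the live one, and both scores are reported.

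The cost is clip preparation and re-reading time, with no added radiation or visits. Raters who were present live may recall some clips; shuffling across infants reduces this but does not remove it. Masked and live scores may disagree, which is why both are kept. Masking does not correct for the fixed order of conditions or for the selection of infants at CS1.
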